22	BUDGET AND FUNDING IN-KIND SUPPORT	26
23	DISSEMINATION.....	26
24	REFERENCES.....	27
24.1	Eligibility Checklist.....	30
24.1.1	PARTICIPANT ELIGIBILITY CRITERIA.....	30
24.2	Participant Information Form	32
24.3	Participant Consent Form	35
24.4	Data Collection Form	36
24.5	Participant Withdrawal Form.....	41
24.6	Participant Survey – STUDY TWO	42
24.7	Participant Information Form – STUDY TWO.....	45
24.8	Participant Consent Form – STUDY TWO.....	48

SUMMARY OF CHANGES TO THIS VERSION

Section	Change	Reason for update
Version	Version 3 to version 4.0	Investigator changes
Contents page	Addition of section “Summary of Changes to this Version”	Clarity
1. Clinical investigation plan summary – part one	Addition and deletion of investigators	UQ team leaves project, staff turnover
9. Confidentiality	Change UQ HREC to Bellberry HREC	Error correction
14. Clinical investigation plan summary – part two	Addition and deletion of investigators, reference to “The University of Queensland” deleted	UQ team leaves project, staff turnover
15.8. Recruitment	References to “The University of Queensland” and “UQ School of Psychology” deleted	UQ team leaves project
19 Confidentiality	Change UQ HREC to Bellberry HREC, change the University of Queensland to Brisbane Hand and Upper Limb Research Institute	Error correction, UQ team leaves project
24.2 Participant Information Form	Addition and removal of investigators, change of project contact, references to the University of Queensland deleted	UQ team leaves project, staff turnover
24.2 Participant Information Form	Expected date of study conclusion changed from 2018 to 2019	Updated estimate
24.3 Participant Consent Form	References to the University of Queensland deleted	UQ team leaves project
24.5 Participant Withdrawal Form	Addition and removal of investigators, change of project contact	UQ team leaves project, staff turnover
24.6 Participant survey – STUDY TWO	Change of contact email, expected date of study conclusion changed from 2018 to 2019	UQ team leaves project, updated estimate
24.7 Participant Information Form – STUDY TWO	Addition and removal of investigators, change of project contact, references to the University of Queensland deleted, expected date of study conclusion changed from 2018 to 2019, change of project contact	UQ team leaves project, staff turnover, updated estimate
24.8 Participant Consent Form – STUDY TWO	references to the University of Queensland deleted	UQ team leaves project

1 CLINICAL INVESTIGATION PLAN SUMMARY – PART ONE

TITLE	Prediction of post-operative cognitive decline following shoulder surgery in the beach chair position: the value of cerebral oximetry.
INVESTIGATORS	Principal: Associate [name], [name], [name], [name] Associate: [name], [name], [name], [name], [name]
OBJECTIVES	Primary aim: To examine the relationship between cerebral desaturation during shoulder surgery in the beach chair position, and post –operative cognitive decline. Secondary aims: 1. To determine the variation in cerebral oxygenation recorded using simultaneous application of the INVOS™ and FORE-SIGHT® oximeters, during shoulder surgery in the beach chair position. 2. Assess the relationship between cerebral oxygen desaturation and mean arterial pressure, incidence of nausea / vomiting, duration of hospital stay, BMI, hypertension and adverse events.
STUDY DESIGN	A prospective cohort study.
SITES	Brisbane Private Hospital.
NUMBER OF SUBJECTS	Approximately 200 participants will be recruited to this study.
TARGET POPULATION	Participants will be adults who require shoulder surgery in the beach chair position.
LENGTH OF CLINICAL INVESTIGATION	It is anticipated that this study will require 27 months from commencement of recruitment to final data collection phases (24 month recruitment period). The primary end point of the study will be 3 months post-surgery. Participants will be assessed 1 day prior to surgery (baseline), at day 1 post-surgery (early), between 10 & 14 days (mid), at 1 month (late) and at 3 months post –surgery (late).
OUTCOMES	Primary Post- operative cognitive decline will be defined as a drop of 1 standard deviation or more from baseline on 2 or more neuropsychological indices (Tournay-Jette et al., 2011). The following neuropsychological tests will be used; 
• Logical memory test• Trail making test: Delis-Kaplan Executive Function System• Single letter verbal fluency• Stroop test: Victoria’s version• List Learning: Rey Auditory Verbal Learning Test• Letter-Number Sequencing (from Wechsler Adult Intelligence Scale, 4th edition).

	
Secondary Frequency of cerebral desaturation events (CDE) measured (INVOS™ vs FORE-SIGHT®). Cerebral desaturation will be defined as a decrease in rSO2 greater than, or equal to 20% from baseline or a fall below 50% absolute (after Murphy et al., 2010; Salazar et al., 2013). Variables associated with this outcome include:
 
 • Mean Arterial Pressure (mmHg) • BMI • Hypertension • Nausea and Vomiting – within 48 hours • Duration of hospital stay • Adverse Events
--	---

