3.2 STUDY ONE

3.3 AIM OF THE STUDY

This study has three aims;

- (i) To examine the relationship between cerebral desaturation during shoulder surgery in the BCP, and the incidence of POCD.
- (ii) To determine the variation in cerebral oxygenation recorded using randomised (for superior/inferior) simultaneous application of the INVOS™ and FORE-SIGHT® oximeters, during shoulder surgery in the beach chair position.
- (iii) Assess the relationships between cerebral oxygen desaturation during shoulder surgery in the BCP and variables including mean arterial pressure, incidence of nausea/vomiting, duration of hospital stay, BMI, hypertension and adverse events.

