3.6 PRIMARY HYPOTHESES

The primary research hypotheses are;

- (i) Cerebral desaturation events during surgery in the BCP will be related to POCD.
- (ii) The INVOS™ 5100 and the FORE-SIGHT® monitors will show no significant difference in their ability to measure cerebral oxygenation.
- (iii) Cerebral desaturation events experienced during shoulder surgery in the BCP are related to a drop in mean arterial blood pressure, an increased likelihood of post-operative nausea and vomiting, greater length of hospital stay, a higher BMI, hypertension and greater frequency of adverse events.

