7.2.3 DATA COLLECTION FORMS FOR PRIMARY AND SECONDARY HYPOTHESES

Primary and secondary outcomes will be recorded for each participant on their data collection form. This form will include demographic, clinical and outcome data (24.4). The primary outcome to be measured is the incidence of Post-operative Cognitive Decline. This has been defined as a drop of 1 standard deviation or more from baseline on 2 or more of the neuropsychological indices included. The secondary outcome to be measured is the incidence of cerebral desaturation as well as the importance of other key clinical variables (e.g. blood pressure, nausea, body fat etc).

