10.1 STATISTICAL METHODS

Baseline demographic and clinical data will be examined using descriptive statistics (means, standard deviations [SDs], and percentages). Dropouts will be compared to those who complete the study. For initial data screening, descriptive statistics (means, standard deviations [SDs], and percentages) will be completed for all predictor and outcome variables. Based on the findings of de Tournay - Jette et al. (2011), we assume that 62% of patients will not experience desaturation, and that the probability of postoperative cognitive dysfunction in these patients is 29%. To observe an increased risk of cognitive dysfunction of 1.75 times in patients who experienced desaturation (i.e. to 50%) we will be required to collect postoperative data on 193 participants, assuming $\alpha=0.05$ and $\text{power}=80\%$. For the secondary outcome, which is the concordance between the INVOS™ 5100 and FORE-SIGHT® devices during shoulder surgery, the agreement between these pairs of observations will be assessed using intra-class correlation (ICC 3,1) (Portney & Watkins, 1993).

A number of statistical analyses will be used to explore the relationship between CDE and other study variables to allow for use of continuous and categorical data (e.g. linear & logistic regression). With an anticipated sample size of 200 this should provide adequate numbers for our analysis (Portney & Watkins, 1993). Prior to the use of a regression analysis, exploratory bivariate analyses (e.g. correlation, chi square, one-way ANOVA) will be conducted among all predictor variables to identify multi-collinearity. Bivariate analyses between each predictor and outcome variable will then be conducted. Significant predictor variables identified from bivariate analyses will be entered into the regression model. A process of backward elimination will then be used to identify the best model considering main effects and two-way interactions at $p \leq 0.05$. Data analysis will be conducted using SSPS version 23. Any complication rates will be reported in terms of frequency and analysed. The potential contribution of type of surgery, the length of surgery and the nature of the anaesthetic agents

used are recorded as standard practice and will be included in analyses to assess whether or not they represent confounding factors. The final multivariable model will include the main effects of interest and variables identified as potential confounders.

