The type and duration of anaesthesia is being recorded (see 15.4). Although the choices of anaesthetic medications and techniques may affect the incidences of cerebral desaturation event, they do not have any impact on correlating cerebral desaturation events, should they occur, and the postoperative metrics we are seeking to measure other than the secondary outcomes of pain and postoperative nausea and vomiting. By recording these additional data sets we will seek to ascertain any confounding effects they may have on the pain and postoperative nausea and vomiting but they will not be relevant to cerebral desaturation events since we are looking at the effects of the cerebral desaturation events rather than their incidence.

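### Aim (iii) treats desaturation as an outcome in one place and as an exposure in another, and the regression rule sets no timing limit that would keep its consequences out of a model of its risk factors

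*Protocol*

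**What the plan says.** **CDE as outcome.** The Outcomes entry in section 1 of the protocol makes CDE frequency the secondary outcome. Under the line "Variables associated with this outcome include" it gives one undivided list: MAP, BMI, hypertension, "Nausea and Vomiting – within 48 hours", duration of hospital stay and adverse events. Section 7.2.3 agrees: "The secondary outcome to be measured is the incidence of cerebral desaturation as well as the importance of other key clinical variables".

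**No direction.** Aim (iii) in section 3.3 reads "Assess the relationships between cerebral oxygen desaturation during shoulder surgery in the BCP and variables including mean arterial pressure, incidence of nausea/vomiting" and continues with the same mixed list. Hypothesis (iii) in section 3.6 links CDE to a fall in MAP and to "an increased likelihood of post-operative nausea and vomiting, greater length of hospital stay, a higher BMI, hypertension and greater frequency of adverse events", all in one sentence.

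**CDE as exposure.** The last paragraph of section 10.1 states that "we are looking at the effects of the cerebral desaturation events rather than their incidence", and it classes pain and postoperative nausea and vomiting as secondary outcomes.

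**The modelling rule.** Section 10.1 proposes linear and logistic regression to explore how CDE relates to other variables. Each predictor is screened against the outcome, and then "Significant predictor variables identified from bivariate analyses will be entered into the regression model", followed by backward elimination with two-way interactions at p ≤ 0.05. The paragraph closes by saying that the final model will hold the main effects of interest and potential confounders.

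**The concern.** BMI and a history of hypertension exist before the operation, so they can be studied only as predictors of whether a CDE occurs. Nausea, vomiting and length of stay are entered on the Post-Operative Record and follow an intra-operative CDE, so they cannot predict it. A protocol that puts both kinds of variable under one outcome, and elsewhere denies that incidence is of interest, does not say which way each aim (iii) model runs.

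This matters because the entry rule works on significance alone. If hypothesis (iii) is true, nausea and stay are associated with CDE and will tend to pass the bivariate screen. Entered beside BMI or hypertension in a model for CDE, they can shift those coefficients. A real risk factor could look weaker or disappear, and a null one could look protective.

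**Working it through.** **1. The passages side by side**

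| Place | Role of CDE | Role of nausea/vomiting |
|---|---|---|
| Section 1, Outcomes | secondary outcome | variable listed under CDE |
| Section 7.2.3 | secondary outcome (incidence) | other clinical variable |
| Sections 3.3 and 3.6 | no direction | no direction |
| Section 10.1, last paragraph | exposure; incidence disclaimed | secondary outcome |

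Rows 1 and 2 cannot govern aim (iii) together with row 4. This conflict needs no arithmetic.

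**2. The plan's own figure**

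Aim (iii) has no sample-size figure. The 193 in section 10.1 belongs to the primary comparison: 29% against 50% with a 62:38 split, α = 0.05 (taken as two-sided) and 80% power. A continuity-corrected two-proportion formula gives 122 in the no-CDE group and 122 × (1 + 38/62) = 197 in total, within 3% of 193. Without the correction the total is 178. Nothing below changes this figure.

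**3. When a consequence in the model biases a risk factor**

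The effect sizes here are assumptions; the documents give none. Measure stay S in units of its residual SD:

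- logit P(CDE | BMI) = α + β·BMI
- S = a·CDE + b·BMI + e, with e standard normal (up to a constant)

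Bayes' rule then gives

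logit P(CDE | BMI, S) = α + β·BMI + a·(S − b·BMI) − a²/2,

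so the BMI coefficient becomes **β − a·b**. Nausea that depends on CDE only adds a term in nausea and leaves the BMI coefficient alone. With β = ln 1.50 = 0.4055:

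| a (CDE on stay) | b (BMI on stay, direct) | β − ab | BMI odds ratio |
|---|---|---|---|
| 0.5 | 0.3 | 0.4055 − 0.15 = 0.2555 | 1.29 |
| 0.8 | 0.5 | 0.4055 − 0.40 = 0.0055 | 1.01 |
| any | 0 | 0.4055 | 1.50 |
| 0 | any | 0.4055 | 1.50 |

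If BMI has no effect on CDE (β = 0), the first two rows become exp(−0.15) = 0.86 and exp(−0.40) = 0.67. Simulation with nausea and stay both entered gave the same range for a true 1.50 (1.29 down to about 1.0).

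**4. Three consequences entered together**

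A second simulation (400,000 records per scenario, true BMI odds ratio 1.5) entered nausea/vomiting, stay and adverse events. For stay, half the log odds ratio was used as the linear effect.

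| CDE → consequence OR | BMI → consequence OR (direct) | BMI OR for CDE |
|---|---|---|
| 2 or 3 | 1 | 1.5 |
| 2 | 1.5 | 1.26 |
| 2 | 2 | 1.14 |
| 3 | 1.5 | 1.14 |
| 3 | 2 | 0.95 |

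Hypertension, given no direct path to the consequences, stayed near its true 1.5 throughout. Results were essentially the same with CDE prevalence near the protocol's 38% (100% − 62%) and at the 18% (9/50) it cites from an earlier beach-chair study.

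**5. Is a direct path plausible here?**

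For BMI and stay, the documents are silent. For anaesthetic choice, section 10.1 accepts a possible effect on CDE incidence and plans to examine its effect on pain and nausea/vomiting. That is the structure in which entering nausea would distort the anaesthetic coefficient.

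**The case against.** A reader might infer that the protocol prescribes conditioning on consequences and so biases the BMI, hypertension and MAP estimates. The documents do not support that, for four reasons.

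- **No dependent variable is named.** Section 10.1 leaves the direction of aim (iii) open. Its mention of linear regression suits length of stay as an outcome, and its last paragraph treats nausea/vomiting as one. The section 1 line is a synopsis heading, not a model specification.
- **The closing sentence points the other way.** A consequence of CDE is not a confounder of BMI and CDE. Read strictly, limiting the final model to main effects and potential confounders would exclude it. The sentence does not expressly bar post-CDE variables, however, and it follows a rule that admits whatever is significant.
- **Bias is conditional.** It needs a path from the risk factor to the consequence that bypasses CDE. Without one, the odds ratio does not move.
- **The split into causes and consequences is not clean.** MAP is recorded simultaneously with oximetry (sections 2 and 6.1). Adverse events are recorded during surgery as well as at follow-up (sections 6.1 and 8.4).

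A single figure for lost power is also tempting but would mislead. At n = 200 and 0.5 log-odds per SD, power to detect BMI with the consequences entered was about 87% with no direct path, about 50% at the mild end of the assumptions and about 10% at the strong end.

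The planned bivariate analyses are not affected by this conditioning. Covariate lists for secondary models may properly be left to a statistical analysis plan, which is not shown here. All of this limits the size of the claim. It does not remove the conflict between sections 1 and 7.2.3 and the end of section 10.1, which stands in the protocol itself.

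**Conclusion.** The protocol contradicts itself on whether aim (iii) studies the incidence of CDE or its effects. Its variable list mixes earlier, concurrent and later measurements, and its entry rule permits, without requiring, later ones in a model for CDE. That part rests on the text alone.

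The size of any resulting bias rests on assumption. With CDE lengthening stay by 0.5-0.8 SD and BMI directly lengthening it by 0.3-0.5 SD, a BMI odds ratio of 1.50 per SD falls to about 1.0-1.3. With no direct path it stays at 1.50. It does not follow that hypertension or MAP estimates are distorted, or that aim (iii) will be answered wrongly. The aim is secondary and exploratory, but the correction is nearly free.

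**What to change.** Split aim (iii) by direction in sections 1, 3 and 10.1.

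- **(a) CDE as outcome.** Admit only variables that precede it: BMI, hypertension, MAP before the first CDE, and surgical and anaesthetic factors set before it. State which stretch of the MAP record is used in patients without a CDE.
- **(b) CDE as exposure.** Fit separate models for nausea/vomiting, length of stay, and adverse events with onset after the CDE, each adjusted for pre-CDE variables only. State the corresponding time window for adverse events in patients without a CDE.

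Do not enter any (b) outcome as a predictor in an (a) model, whatever its bivariate p-value. Reconcile the last paragraph of section 10.1 with sections 1 and 7.2.3, so that incidence is either an outcome of interest or is not.

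The cost is wording and a few more models. The time-stamped oximetry and MAP recordings already planned allow the ordering, no new data are needed, and the 193 required for the primary comparison does not change.

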2 INTRODUCTION

The “beach chair position” (BCP) has been used to perform shoulder surgery since the early 1980s and has several cited advantages compared to alternative positions. These include; reduced strain on the brachial plexus, less risk of neurovascular injury compared to a lateral decubitus approach and excellent intra-articular visualization (Murphy et al., 2010). However, despite these advantages and the widespread use of this position during shoulder surgery, the BCP has also been associated with some rare but severe adverse clinical outcomes. These have included; ischaemic brain and spinal cord injury, stroke, visual loss and ophthalmoplegia (Pohl & Cullen, 2005; Murphy et al., 2010). This has highlighted the need to routinely monitor cerebral oxygenation during shoulder surgery in the beach chair position and has prompted the development of clinical protocols to minimise the effect of cerebral desaturation events (CDE) (Closhen et al., 2013; Salazar et al., 2013).

It has been hypothesized that a combination of factors may contribute to the increased risk of CDE occurring in the BCP. Normal physiological changes associated with sitting upright are magnified in the context of a general anaesthetic. Venous return is reduced by the effect of gravity and compromised further by vasodilation and the myocardial depressant effect of anaesthesia. In the non- anaesthetised patient, changes in the sympathetic nervous system produce an increase in systemic vascular resistance to counteract the effect of gravity. This modulation of haemodynamics via the autonomic nervous system is lost in the anaesthetised patient increasing the risk of cerebral hypoxia (Pohl & Cullen, 2005).

The relationship between CDE and post- operative cognitive decline (POCD) is not well understood (Lopez et al., 2013). Little is known about the significance of the type and duration of CDE and whether or not this has any bearing on cognitive outcome. Some authors continue to question the relationship between CDE and subsequent cognitive impairment (Parra et al., 2011; Zheng et al., 2013; Kok et al., 2014). Salazar et al., (2013) provide the only study that examines the relationship between CDE in shoulder surgery using the BCP and subsequent cognitive impairment. These authors did not find a statistically significant relationship between CDE and cognition as assessed using the “Repeatable

Battery for Assessment of Neuropsychological Status “(RBANS) with either composite scores or using the sub-indices. They attribute this lack of significant findings to insufficient study power. The incidence of cerebral desaturation in their study was 18% (9/50 participants). In contrast, de Tournay-Jette et al, (2011) found a significant relationship between CDE and POCD in elderly patients following coronary artery bypass graft surgery. These authors used a detailed battery of neuropsychological assessments and highlight the need for sensitive assessments of cognitive function.

This difficulty in clarifying the relationship between CDE and POCD may be further compounded by our ability to accurately measure cerebral perfusion. To date, no clear definition of cerebral ischaemia exists and little is known about individual patient factors (e.g. pre-existing cerebral vascular disease) that may influence cognitive outcome (Murphy et al., 2010). Additionally, changes in the proportion of venous versus arterial components of blood pressure will vary with changes in body position. This is not necessarily reflected in the observed change in overall oxygen concentration (Murphy et al., 2010). Individual variation in acceptable mean arterial blood pressure has also been reported. Whilst 50mmHg is generally the accepted level, the required level in some cases has been found to be as high as 70-80mmHg (Murphy et al., 2010). Hence, the conditions leading up to a CDE associated with cognitive impairment may vary from one patient to another and are influenced by patient specific characteristics (Murphy et al., 2010).

A number of cerebral oximeters are commercially available. Douds et al. (2014) completed a systematic review of devices commonly used in cardiac surgery and concluded that there were only a very limited number of high quality papers available. Most of these papers were based on the INVOS™ system. These authors highlighted the need for further RCTs to investigate the role of cerebral oximetry and the efficacy of devices currently available. Hessel et al., (2014) examined cerebral oxygenation in newborns using both the FORE-SIGHT® and INVOS™ monitors. They found that the FORE-SIGHT® monitor demonstrated greater repeatability and hypothesised that this may indicate a lower responsiveness to change in oxygen saturation. In contrast, Closhen et al., (2013) compared the use of the INVOS™ and FORE-SIGHT® monitors to detect oxygen saturation in the beach chair position and found no significant difference according to monitor type. The study by Bickler et al., (2013) compared the performance of several cerebral oximeter devices including the FORE-SIGHT® and INVOS™ monitors. It compares the performance of different cerebral oximetry devices using an invasive reference standard and a common sample population (health adult volunteers), simultaneous testing methodology and data analysis. It is important that the monitors are being used within their approved indication for and that care must be taken to avoid optical cross-talk between the sensors of different manufacturers. In addition, the sensors will be placed randomly on the forehead in terms of superior and inferior in the same position to avoid sequential bias. Both the FORE-SIGHT® and INVOS™ cerebral oximetry measurements have been assessed and shown to be valid surrogates for true cerebral oxygenation .

Monitoring cerebral oxygenation in the BCP is an area of evolving attitudes in regards to standard of care. There are many hospitals in Australia who have now adopted cerebral oximetry as a standard of care for monitoring patients in the beach chair position. It is the feeling of all of the surgeons involved in the investigation that in fact, cerebral oxygenation monitoring is part of an adequate standard of care for patients in the beach chair position and it is routinely utilised currently in all beach chair position surgeries. It is not expected that there will be any significant alteration to operative time by placing two oxygen monitors and there is certainly no risk to the surgeon, anaesthetist or the nursing team. Data is recorded using monitors that output the data digitally and all of the data will be compared using standard timestamp methods so that they can be directly compared. The oximetry and MAP data will be simultaneously digitally recorded for the research data collection and analyses.

In conclusion, the relationship between shoulder surgery in the BCP and cerebral oxygenation is suggestive and requires further investigation. In addition, factors associated with cerebral desaturation and the incidence of POCD are not well understood. The value of cerebral oximetry in predicting CDE and POCD remains unclear. Further research in these areas is indicated and the proposed study aims to address the issues raised here.

